6.1.3 Other study parameters (if applicable)

Before the treatment is initiated we will assess the level of treatment resistance with the DM-TRD (Peeters 2016; Ruhe 2012).

[figure not shown]

Figure 2. Outline of the Pavlovian to instrumental transfer (PIT) task - Instrumental training. To centre the cursor, participants click in a central square. The experiment consists of a first block with exclusively instrumental approach trials ($n=120$) and a second block with exclusively withdrawal trials ($n=120$). In approach trials (top), participants chose whether to move the cursor towards the mushroom and click inside the blue frame onto the mushroom (go), or do nothing (nogo). In withdrawal trials, they instead move the cursor away from the mushroom and clicked in the empty blue frame (go) or do nothing (nogo). Outcomes are presented immediately after go actions, or after 1.5 seconds. Per block there are 3 “good” and 3 “bad” instrumental stimuli. Participants play each block once per testing day. Instrumental stimuli are different for both blocks and both days. **Pavlovian training.** Participants passively view stimuli and hear auditory tones, followed by wins and losses. There are five fractal/tone combinations. Each combination is displayed 12 times in the first block and another 6 times in the second block. **Pavlovian-instrumental transfer.** Participants respond to the instrumental stimuli trained during the instrumental training stage, with Pavlovian stimuli tiling the background. No outcomes are presented, but participants are instructed that their choices count towards the final total. No explicit instructions about the contribution of Pavlovian stimuli towards the final total are given.

2. Pavlovian to Instrumental Transfer Task

In this task (see Figure 2) we assess to what degree instrumental behavior of participants is influenced by previously learned Pavlovian stimuli-outcome associations. To do this, we first train subjects to react to instrumental stimuli (IS) to earn money. In this phase, participants are asked to approach the stimuli with positive outcome by clicking on them. Next, we show subjects neutral pictures that we then associate with monetary wins and losses. By this latter classical (or Pavlovian) conditioning procedure these neutral pictures acquire an affective valence and become conditioned stimuli (CS) with appetitive and negative valence respectively. Then we ask subjects to react to the IS again, but now also show them the CS. Afterwards, the participants are again trained to react to instrumental stimuli, but now the participants need to make withdrawal responses, where they need to click on the stimuli to put them away and where they “collect” the stimuli when they do not respond. Again, this is followed by the task where the IS and CS are shown together

and participants need to respond to the IS in the learned manner. Previously we have shown, that these CSs can invigorate or inhibit behavior dependent on the valence of the CS (appetitive vs. negative): for example, the appetitive CS promotes and the negative CS inhibits approach actions (Geurts, Huys, den Ouden, et al., 2013; Huys et al., 2011).

Hypothesis:

We aim to deliver a prediction model that relates closely to the mechanisms underlying TRD and to the mode of action of s-ketamine for which PIT is the foremost candidate. First, s-ketamine indirectly influences ascending monoaminergic pathways via neural firing in the brain's 'anti-reward center', the lateral habenula. Second, these monoaminergic pathways are implicated in using emotional information to guide goal-directed behavior. Disturbances in this behavioral guidance are key to the negative self-reinforcing mechanisms found in TRD: e.g. increased avoidance and blunted approach behavior in resp. negative and positive contexts. Thus, a test that quantifies affect-driven avoidance and approach behaviors would carry great potential in predicting the effect of s-ketamine on TRD. The Pavlovian to instrumental transfer test (PIT), is exactly the right test, which indeed has been shown to predict recovery of depression (Huys, 2016) and is widely used in psychiatric disorders (see for review Garbusow, 2022). Moreover, it quantifies guidance of avoidance and approach behaviors by affective information, which has been related to depression (Huys 2016, Nord, 2018, Geurts 2023a *in preparation*) and is dependent on monoaminergic signaling (Geurts 2013, Geurts 2023b *in preparation*). Thus, we hypothesize that this test, in conjunction with conventional, clinical predictors, can help us stratify and predict individual treatment effects, thus advancing clinically applicable precision psychiatry.

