1. STUDY DESIGN

This is an unblinded cohort study of patients who are treated with intranasal esketamine (open label). This cohort is a cohort study of real world regular treatment with esketamine intranasal administration. For the objectives of this study, no other routines or interventions will be applied apart from the necessary measurements used for optimal clinical care and decisions about effectiveness and acceptability, except for the PIT task. All data, except for the PIT task, can be obtained from the clinical medical records of the patients, who will provide informed consent for the data-collection as described in this protocol. Data from the PIT task will be collected via online testing using Gorilla (cf. 'Online testing' covered under CMO2014/288).

Figure 1.

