3.2 Use of co-intervention (if applicable)

Patients will continue their antidepressant medication (SSRI, SNRI, TCA), which might be optimized according to dosage or therapeutic drug monitoring (if appropriate).

If possible, a maximum of 3 mg lorazepam (or equivalents) daily is used, and preferably stopped during the treatment.

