6.1.2 Secondary study parameters/endpoints

Secondary endpoints are:

- The change (relative to baseline) in clinician-rated MADRS score (Montgomery 1979) over time measured in 4 weeks intervals after week 8.
- The change (relative to baseline) in self-rated IDS-SR score (Rush 1996; Trivedi 2004) at 4 weeks and over time measured in 4 week intervals thereafter.
- Quality of Life measurement (EQ-5D-5L; Janssen 2013) at 4 weeks and over time measured in 4 week intervals thereafter (relative to baseline)
- Level of functioning at 4 weeks (WHODAS-2.0; Forero 2018) and over time measured in 4 week intervals thereafter (relative to baseline)
- Cost-effectiveness (modified TiC-P) at 4 and 8 weeks and 3 monthly intervals thereafter (relative to baseline)
- The change in mood (before-after) esketamine intranasal spray per session as measured by a visual analogue scale before administration and after completion of the session (before leaving).
- Occurrence of adverse effects including dissociative symptoms at T=40 min after administration (or as close as possible) and at the end of the session as measured with the KSET (Short 2020) per session
- Discontinuation rates: due to adverse effects of the treatment or other reasons.
- Changes in blood-pressure during esketamine intranasal sessions (baseline, 10, 40, 90 minutes)
- Follow-up 3 months after discontinuation of intranasal esketamine treatment.

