6.2 Randomisation, blinding and treatment allocation

N/A

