Following the STROBE22 guideline, we will build a model to predict response in terms of depressive symptom reduction after 4 weeks of treatment with esketamine intranasal sprays. Clinical and computational parameters from PIT (easy to administer, web-based test measuring the influence of affect on reward-driven behaviors), collected before treatment initiation in 350 TRD patients, will be used as predictors. To predict response based on multiple predictors (PIT, questionnaire, demographical, clinical data) I will follow TRIPOD(-AI) guidelines and use common machine learning procedures (i.a. support vector machine, penalized regression and tree-based approaches) with cross-validation to prevent overfitting. The best algorithm in terms of precision-recall area under the curve will be tested on a hold-out test dataset (not involved in algorithm tuning) against at least reasonable specificity (90%) for non-response, making it acceptable for clinical purposes. As external validity is very important (and often not taken into account) in translational research, we will test algorithms again through continuous data collection and assess clinical utility with common test-statistics. Test data will be used to optimize algorithms iteratively, by further hyperparameter tuning (test and tune procedure).

For each separate analysis done in this consortium, we will pre-register an analysis plan at the Open Science Framework (<https://osf.io/>)

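### The single-arm cohort can predict response during esketamine treatment, but not individual treatment effects or cost-effectiveness, as the hypothesis and one secondary endpoint are worded

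*Protocol*

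**What the plan says.** Protocol section 1 describes the design: "This is an unblinded cohort study of patients who are treated with intranasal esketamine (open label"). Under the heading "6.2 Randomisation, blinding and treatment allocation" the entry is N/A. No untreated, alternatively treated or external group is named anywhere in the protocol.

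The hypothesis in section 6.1.3 uses the language of treatment effects. It says that a test of affect-driven approach and avoidance "would carry great potential in predicting the effect of s-ketamine on TRD", and ends with the expectation that the PIT, together with conventional clinical predictors, "can help us stratify and predict individual treatment effects, thus advancing clinically applicable precision psychiatry".

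Section 8.3 then states the analysis: "we will build a model to predict response in terms of depressive symptom reduction after 4 weeks of treatment with esketamine intranasal sprays". The third aim in the Summary, repeated as a secondary objective in the Objectives section, is to use the predicted response for pre-selection.

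Section 6.1.2 lists among the secondary endpoints "Cost-effectiveness (modified TiC-P) at 4 and 8 weeks and 3 monthly intervals thereafter (relative to baseline"). The Summary also names cost-effectiveness as a secondary outcome. Section 3.2 says of the continuing antidepressant that it is a treatment "which might be optimized according to dosage or therapeutic drug monitoring (if appropriate"); section 6.3 repeats the point.

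**The concern.** An individual treatment effect is the difference between a patient's outcome with esketamine and the same patient's outcome without it. Here only the first is ever observed. A model fitted to these data learns who improves while on esketamine. It cannot learn who improves because of it. The hypothesis and the planned analysis therefore have different targets, and the data support only the second.

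This matters because the model is meant for pre-selection. If its output is read as predicted benefit, a low predicted response will be taken to mean that the patient gains little from esketamine, which these data cannot show.

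The cost endpoint has the same gap. Cost-effectiveness compares costs and effects under one option with those under another. A contrast with the patient's own baseline contains natural course, possible regression to the mean and any antidepressant optimisation, along with whatever esketamine contributes.

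**Working it through.** The protocol gives no figure to reproduce: section 2.4 states that no power calculation was made, and the question is one of identifiability. All numbers below other than n=350 (section 8.3) are assumptions chosen for illustration.

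**1. Prediction of effect.** Let x be a standardised baseline predictor, Y1 the MADRS improvement at week 4 with esketamine and Y0 the improvement without it. The individual effect is d = Y1 − Y0. Assume Y1 = 12 + 4x + e, with e of SD 9, and count response as Y1 ≥ 15.

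- World A (x purely prognostic): Y0 = 6 + 4x + e, so d = 6 for everyone.
- World B (x modifies the effect): Y0 = 6 + e, so d = 6 + 4x.

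The mean effect is 6 in both worlds. Over 2,000 simulated cohorts of 350:

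| | AUC for response on treatment | Correlation of x with true effect |
|---|---|---|
| World A | 0.688 | 0 (effect constant, so set to 0) |
| World B | 0.688 | 1.0 |

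The AUCs agree because Y1 has the same distribution given x in both worlds. A larger cohort, a hold-out set or a better algorithm cannot change that, since each uses Y1 and x only.

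For one patient with x = −1.5, expected improvement on treatment is 12 + 4(−1.5) = 6. In World A the expected improvement without esketamine is 6 + 4(−1.5) = 0, so the effect is 6. In World B it is 6, so the effect is 0. The same prediction fits a patient who gains as much as anyone else and a patient who gains nothing.

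**2. Cost-effectiveness.** The incremental ratio is (C1 − C0)/(Q1 − Q0), where 1 is esketamine and 0 the alternative. Assume C1 = 15,000 and Q1 = 0.10 QALY, and vary the unobserved C0 and Q0:

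| Q0 | C0 = 0 | C0 = 5,000 |
|---|---|---|
| 0 | 150,000 | 100,000 |
| 0.03 | 214,286 | 142,857 |
| 0.06 | 375,000 | 250,000 |
| 0.09 | 1,500,000 | 1,000,000 |

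For example, (15,000 − 0)/(0.10 − 0.09) = 1,500,000 and (15,000 − 5,000)/(0.10 − 0) = 100,000. With the treated patients' data held fixed, the ratio varies 15-fold. Taking baseline as the reference amounts to assuming that costs and utility would have stayed at baseline without esketamine, which the cohort cannot check.

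**The case against.** The strongest reply is that the wording at fault is a hypothesis in a rationale, while the analysis in section 8.3 is sound. That stands in part. A reader might infer that the prediction model itself is invalid; it is not, since response after four weeks on treatment is a legitimate target in a single-arm cohort. The third objective already speaks of predicted response rather than effect, so it needs a caveat, not a new target. What remains is that section 6.1.3 promises more than section 8.3 delivers, and that pre-selection is where the two are most easily confused.

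A second reply is that the protocol never mentions an incremental ratio, and that the plans to be pre-registered for each analysis (section 8.3) could supply an external or modelled comparator. They could. But the protocol itself names the endpoint cost-effectiveness and fixes baseline as its reference, and a later plan would have to depart from that text.

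Some stronger readings are not supported:

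- That regression to the mean is certain because patients enter severely ill. Section 2.2 requires treatment resistance and sets no minimum symptom score, so regression to the mean is only possible.
- That a purely prognostic association is what the protocol leads one to expect. Section 6.1.3 does say of the PIT that it is a test "which indeed has been shown to predict recovery of depression", but the cited study is not at hand, and the same section gives a mechanism specific to s-ketamine.
- That the tool would exclude patients who gain most. This is a conjecture about later use. Section 8.3 plans hold-out testing, a 90% specificity requirement for non-response and an assessment of clinical utility. These steps do not identify a treatment effect, but they bear on how readily the tool would be applied.
- That restricting the analysis to patients whose medication did not change would solve the problem. It supplies no untreated outcome, and it selects on decisions after baseline that may depend on early response.

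**Conclusion.** The concern holds as a mismatch between what two passages claim and what the design can show. The hypothesis in section 6.1.3 goes beyond the analysis in section 8.3, and the cost endpoint in section 6.1.2 carries a label that a before-after contrast cannot meet. Non-identifiability rests only on two facts in the protocol: everyone is treated and no comparator is named. The AUC of 0.688 and the ratio range of 100,000 to 1,500,000 rest on assumed inputs and show the nature of the gap, not its size in this cohort. The point touches secondary and exploratory aims. The primary endpoint, MADRS change at 4 and 8 weeks, is unaffected. It should be corrected, but it does not call the study into question.

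**What to change.** Three changes of wording:

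1. In section 6.1.3, replace both statements about predicting effects with *predict symptom response during esketamine plus antidepressant treatment*, in line with section 8.3.
2. Beside the third objective, in the Summary and in the Objectives section, state that the model is prognostic under treatment and supports no inference on who benefits relative to not receiving esketamine.
3. In the Summary and section 6.1.2, relabel the TiC-P endpoint as *costs and health-related quality of life (EQ-5D-5L) during treatment relative to baseline*, with no cost-effectiveness conclusion unless a comparator source is named.

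No new data, visits or analyses are needed. The cost is narrower claims on the secondary and exploratory aims. If the sponsor wants to keep a cost-effectiveness aim, the cost is greater: a comparator source must be named and justified.

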6.2 Randomisation, blinding and treatment allocation

N/A

6.3 Study procedures

All procedures are part of routine clinical practice. No invasive or additional measurements will be done.

Initial assessment for eligibility for esketamine intranasal treatment consists of:

- Assessment of in- and exclusion criteria including determination of DSM-5 diagnosis by either clinical or semi-structured clinical interview.
- Level of treatment resistance (DM-TRD)
- Drug and alcohol screening (if appropriate)
- Pregnancy test (if appropriate)
- Routine ECG and laboratory assessment
- Assessment of baseline MADRS and IDS-SR score

- Internet-based delivery of PIT test via GDPR certified online testing platform Gorilla

After inclusion, patients will continue the antidepressant they are currently using. This treatment might be optimized according to dosing or TDM. Patients start treatment in accordance with the schedule provided by the manufacturer and described under 4.1 (Figure 1).

Every session:

- VAS-ratings of mood will be asked at every session before-after esketamine administration
- Adverse effects including dissociation at 40 minutes after the last dose of esketamine, or – in case of more pronounced dissociation- as close as possible and at the end of the session (KSET)

During the Induction Phase weekly assessments of effectiveness will be done. In the Continuation (maintenance) Phase this will be continued every second week at frequencies of administration $\geq 1/\text{week}$, while if the frequency is $\leq 1/2 \text{ weeks}$, assessments will be done monthly for the first 2 months, followed by every two months thereafter:

- Repeated assessments of MADRS and IDS-SR scores.

Formal evaluations of the treatment will be performed at regular intervals according to clinical judgement. The first evaluation of effectiveness will be after 4 weeks of twice weekly administration. This will also be the second and last time that the subject is asked to do the online PIT test.

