3.1 Investigational product/treatment

Treatment will be provided according to the 'TREATMENT GUIDELINES for Esketamine Nasal Spray for the use of treating Physicians' as provided by the manufacturer.

In brief, treatment will be provided initially twice per week during the Induction Phase, followed by a Continuation (maintenance) Phase, where in week 5-8 treatment will be provided once weekly and from week 9 onwards dosing can be tried to be reduced to once every two weeks (Figure 1). Usual initial dosages are 56mg/session, which may be increased to 84mg/session. Especially in elderly the initial starting dose will be lower (28mg/session), and if responsive, patients may stay on that dosage. Dosing frequency will be individualized to the lowest frequency to maintain remission/response. At the end of Induction Phase, evidence of therapeutic benefit (based on the clinician's evaluation of symptomatic change and/or improvement in functioning or quality of life) will be evaluated to determine need for continued treatment in the Continuation (maintenance) Phase. After depressive symptoms improve, treatment is recommended for at least 6 months.

Each treatment session consists of administration of esketamine nasal spray and post-administration observation under the supervision of a healthcare professional. Patients will administer the nasal spray themselves. Because of possible nausea and vomiting after administration of esketamine nasal spray, patients should not eat for at least 2 hours before administration and not to drink liquids at least 30 minutes prior to administration. Patients who require a nasal corticosteroid or nasal decongestant on a dosing day should be advised not to administer these medications within 1 hour before administration of esketamine nasal spray.

All patients remain at the clinical site until safety procedures have been completed (monitoring of blood pressure and dissociative symptoms) and the patient is ready for discharge. Readiness to leave is assessed based on clinical judgement of dissociative symptoms measured 40 minutes after the last dose administered or as soon as possible after the patient wakes up. Patients must not drive a car or work with machines for 24 hours after esketamine dosing, therefore patients need to have transportation home after the procedure.

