8.2 Secondary study parameter(s)

For secondary outcome study parameters (IDS-SR, QoL and level of functioning) we will use a comparable approach as for the primary study outcome.

Discontinuation rates will be described over time, also in relation with level of TRD.

Occurrence of dissociative symptoms and blood-pressure per session will be examined for stability over time. Moreover, the severity of these adverse effects and the variation thereof between patients will be described descriptively.

For the second aim of the project, we aim to pool this data across different treatment centres in order to increase power and obtain more quantitative information about possible characteristics of responders vs non-responders.

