11.2 Synthesis

Use of esketamine intranasal has been studied quite extensively already in TRD-patients and frequencies of adverse effects are moderate, especially during administration dissociative symptoms and increases of blood-pressure might occur which are variable between patients and self-limiting. Pharmacokinetics of esketamine are well known. As long as the manufacturer's precautions and instructions are followed there is a minimal risk involved in this treatment.

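### The 40-minute KSET rating may move off time precisely when dissociation is stronger and still fills the 40-minute endpoint slot, so dissociation is liable to be understated, mainly in its upper tail

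*Protocol*

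**What the plan says.** Protocol 6.3 (Study procedures) asks for a KSET rating at every session, 40 minutes after the last dose. The only stated ground for departing from that time is the strength of the symptom: "in case of more pronounced dissociation- as close as possible and at the end of the session (KSET").

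Protocol 6.1.2 defines the secondary endpoint as "Occurrence of adverse effects including dissociative symptoms at T=40 min after administration (or as close as possible) and at the end of the session". An on-time rating and an off-time rating share one slot, and the second rating of the session comes at its end. The clock here runs from administration, not from the last dose.

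Protocol 3.1, on readiness to leave, refers to "dissociative symptoms measured 40 minutes after the last dose administered or as soon as possible after the patient wakes up".

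Protocol 8.2 sets out two uses of the data. "Occurrence of dissociative symptoms and blood-pressure per session will be examined for stability over time"; and "the severity of these adverse effects and the variation thereof between patients will be described descriptively". On-time and delayed ratings are not distinguished.

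Protocol 11.2 describes the expected course: "especially during administration dissociative symptoms and increases of blood-pressure might occur which are variable between patients and self-limiting".

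**The concern.** A rating time that shifts because of the value being rated is outcome-dependent measurement. Patients with mild reactions are rated at 40 minutes. Those with stronger reactions may be rated at some other time, presumably later, when a self-limiting effect has partly passed. Both values then stand under the same label.

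Acceptability is part of the primary objective, and dissociation is one of the two effects that 11.2 names. If the strongest reactions are softened by the measurement rule, what suffers most is the upper tail and the spread between patients, which 8.2 sets out to describe. The trigger for deferral is not defined, and the Introduction lists more than 30 centres. Deferral practice could therefore also differ between centres and blur the pooled data.

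**Working it through.** The protocol gives no figure on this point, so there is none to reproduce. The check is a reading of the text followed by an illustration on assumed inputs.

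**Text**

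1. *Trigger.* 6.3 ties the departure from 40 minutes to more marked dissociation and to nothing else.
2. *Same slot.* 6.1.2 admits the off-time rating to the 40-minute endpoint.
3. *Direction.* 11.2 calls the effects self-limiting and places them especially during administration. If the deferred rating is later than 40 minutes, it is lower or at best equal. That it is later is an inference, since 6.3 does not say so.
4. *What else could recover the information.* The other KSET rating is at the end of the session. Blood pressure is also taken at 10 minutes, but no earlier or peak rating of dissociation is listed. The protocol gives no maximum delay, no requirement to record the actual time, and no rule for a patient who cannot be rated at 40 minutes.
5. *Clock.* 6.1.2 counts from administration, while 3.1 and 6.3 count from the last dose. With up to three devices per session (4.6), the two can differ.

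**Illustration for mean severity (all inputs assumed)**

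Let p be the share of sessions rated late, r the ratio of their true 40-minute score to that of the others, d the delay in minutes, and h the half-life of the symptom in minutes. The ranges are p 5–20%, r 2–3, d 10–50 and h 20–40. The longest delay, 50 minutes, runs from 40 minutes to the last scheduled blood-pressure reading at 90 minutes.

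- Loss in a delayed score = 1 − 2^(−d/h). This is 16% for d = 10, h = 40, and 82% for d = 50, h = 20.
- Understatement of the mean = p·r·(1 − 2^(−d/h)) / ((1 − p) + p·r).

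| p | r | d | h | Loss in a delayed score | Mean understated by |
|---|---|---|---|---|---|
| 5% | 2 | 10 | 40 | 16% | 0.10 × 0.159 / 1.05 = 1.5% |
| 10% | 2 | 20 | 40 | 29% | 0.20 × 0.293 / 1.10 = 5.3% |
| 20% | 3 | 50 | 20 | 82% | 0.60 × 0.823 / 1.40 = 35.3% |

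The spread is hit harder than the mean. In the middle row a delayed patient's true score is 2 against 1 for the others, a gap of 1. The recorded score is 2 × 2^(−0.5) = 1.41, so the gap falls to 0.41, a loss of 59%, while the mean loses 5.3%.

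**Illustration for occurrence (all inputs assumed)**

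Take 100 sessions. Ten are deferred, all moderate or severe at 40 minutes, and 10 of the other 90 are also moderate or severe. The true rate is 20%. If a share q of the deferred reactions has passed by the time of rating, the recorded number is 10 + 10 × (1 − q).

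| q | 0 | 0.25 | 0.5 | 0.75 | 1 |
|---|---|---|---|---|---|
| Recorded rate | 20% | 17.5% | 15% | 12.5% | 10% |

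The last column requires every deferred reaction to have vanished, which fits poorly with an instruction to stay close to 40 minutes.

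**The case against.** The case against is substantial, and much of it limits the point.

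- *The tolerance is a limit.* Both 6.1.2 and 6.3 ask for a rating as near to 40 minutes as can be achieved. That is not permission to wait for recovery. This stands: with delays of a few minutes the effect on the mean is negligible.
- *The recall window of the KSET is not described.* If the tool asks about the whole session, a late rating need not lose a resolved reaction. This also stands as an open assumption.
- *Handling of off-time ratings may be set elsewhere.* A reader might infer that delayed ratings will be analysed as 40-minute values. The endpoint wording points that way, but no analysis rule says so. An analysis plan that is not shown, or the pre-registered plans promised in 8.3, could use actual times. They could do so only if the times were recorded at the session, so the data-collection part of the point remains.
- *The worst reactions are not shown to be hidden.* A reader might infer this, but 7.2.1 has adverse events recorded when patients report them or staff observe them, 3.1 has every session supervised, and 6.1.2 counts discontinuations due to adverse effects. These sources do not restore the KSET severity that 8.2 describes, but they do mean a marked reaction need not go unrecorded.
- *Sedation.* A reader might join the waking rule in 3.1 to the KSET endpoint. That rule concerns readiness to leave and does not mention the KSET, and the exception in 6.3 names only dissociation.
- *Main risk.* 11.2 names dissociation and blood-pressure increase together, so dissociation is one of two named risks.

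**Conclusion.** The point holds as a risk of understatement, not as a demonstrated bias. The rule makes the rating time depend on severity and merges the result into the 40-minute slot. For self-limiting effects the direction is downward, mainly in the upper tail and in the between-patient variation.

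This rests on three assumptions: that deferral means later, that symptoms are already declining at 40 minutes, and that the KSET captures the state at the time of rating. The documents do not give the share of deferred sessions, the delay or the rate of decline, so the size cannot be derived. The figures of 1.5% to 35% are illustrative only.

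The endpoint is secondary and descriptive, and the primary MADRS endpoint is untouched. This is a cheap improvement to a named safety endpoint. The differing time anchors are a separate inconsistency in the text and need reconciling in any case.

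**What to change.** In 6.1.2 and 6.3:

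1. Record the actual time of the KSET rating relative to the last dose. When it is not done at 40 minutes, record the reason: dissociation, asleep or logistics.
2. Report delayed ratings separately from on-time ratings.
3. Report patients not ratable at 40 minutes because of dissociation as their own category, with those asleep kept separate. Add a sensitivity summary that counts the dissociation category as marked dissociation. Placing every unratable or sleeping patient in the top severity class in the main summary is not advised, because it could bias the result the other way.
4. Reconcile the time anchor between 6.1.2 (administration) and 3.1/6.3 (last dose).

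The cost is two extra recorded items per session across the centres, in a study that abstracts its clinical data from health records, plus a short addition to the endpoint definition. The reported rate of marked dissociation may become less favourable. The change concerns measurement and reporting only.
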